•NH Leadership Teams will engage in limited study support activities, as follows: (1) Mailing an IRB-approved study introduction letter to the legally authorized representative (LAR) of each NH resident with an ADRD diagnosis and providing all NH staff with a study introduction letter.

(2) Collecting and mailing outcome data (e.g., actigraphs at completion of a 7-day measurement period, completed staff ratings of resident sleep global change) to the University of Alabama project office using UA-supplied self-addressed postage-paid mailers from a tracked express mailing service (e.g., UPS).

(3) Assisting in telephone appointment arrangements and logistical support so that study team members can conduct telephone-based informed consent for NH residents who may have capacity to provide their own consent.

•NH leadership teams will not engage in research study tasks which will be completed exclusively by research study team members with appropriate study protection training:

(1) Conducting informed consent with staff, LARs, and residents.

(2) Conducting staff interviews: staff decisions whether or not to participate in interviews will be kept confidential from NH leadership teams to protect staff from potential coercion to participate in research.

Subject Populations and Anticipated Numbers:

(1) NH Residents. Primary outcomes are measured at the level of NH residents. We anticipate enrolling 57 residents (approximately 19 per each of 3 NHs) in this pilot study (R61 phase).

(2) NH Staff.

a. Training and Intervention Participation.

We will invite all NH staff to participate in the training and intervention. In the 3 NHs in this pilot study (R61 phase) we anticipate enrolling 120 NAs, 45 LPNs, 5 RNs, and 30 interdisciplinary treatment team/leadership team members. There are no known risks to the nursing staff associated with the training, intervention, and resident assessment activities requested of the NH staff. These are resident care and quality improvement activities that are fully within their job descriptions.

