For residents with likely mild ADRD (BIMS score above 10) but no lar, the nursing home leadership team and study staff will go directly to the resident to invite their participation and screen their capacity to consent using the same process described above.

All above procedures apply to securing consent for the research study team to have access to NH resident personally identifiable data.

NOTE: the LOCK sleep program does not include any activities that are outside of standard NH practice, therefore NH staff will be free to enroll any NH residents that they believe will benefit into the LOCK sleep program regardless of resident consent status; however the NH leadership team will only be allowed to share with the research study team data for residents who are consented for the study.

- 3. It should be recognized that decision-making capacity may fluctuate, requiring ongoing Y assessment during the course of the research. Is it reasonable to expect that during the course of the research, subjects may lose their capacity to consent or their ability to withdraw?
 - a) Describe what provisions are in place for periodic re-consent. Include the rationale and procedure, the proposed interval, any changes in behavior that might signal the need to re-consent whether or not the proposed interval has elapsed, and any consultative resources that are available for these decisions. Describe the process for re-consent or re-assent, or reassessment of willingness to continue participation.

Re-consenting provisions will not be included because the course of the study is a relatively short 22 weeks (5.5 months), an amount of time in which it is unlikely, although possible, that cognitive capacity will significantly change. Further, the main focus of the intervention is with staff behavior. Staff will be implementing interventions that are considered good standard clinical practice, such as providing meaningful activities during the day to help reduce resident daytime napping and reducing noise and resident interruptions at night to promote uninterrupted sleep. Therefore, is is unlikely, although possible, that resident willingness to continue participation will change over this relatively short amount of time.

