- 7. For clinical studies (of a drug, vaccine, device or treatment), describe any alternative procedure(s) or course(s) of treatment. List important risks and benefits of these alternatives in order to compare to study procedure(s) or course(s) of treatment. This information MUST be included here. Any standard treatment that is being withheld must be disclosed and the information must be included in the consent form.

The intervention described will be implemented NH-wide. The study is a pilot (R61) for the methods for a subsequent randomized controlled trial (R33 -- an incomplete stepped-wedge cluster randomized controlled trial design in which each NH serves as its own control). There will therefore be no alternative treatments. NH residents and their legally authorized representatives will have the right to refuse participation in any portion of their care just as they would with usual NH care, including use of actigraphs and Fitbits. NH staff will have the right to refuse any interviews.

8a. Describe any other physical, psychological, social or legal risks the participant may experience.

No more than minimal risk.

The risks for participants in this trial are minimal. There are no anticipated physical or economic risks associated with this study. There are no psychological risks beyond what was described in Risks sub-item #5 above.

For both NH residents and staff, an unlikely legal or social risk associated with participating in this study would be invasion of privacy in the remote chance that there is a loss or lack of protection of data containing personally identifiable information. These are research risks, not therapeutic risks. The study team will use careful procedures to guard the security and confidentiality of all data.

For both NH residents and staff, a potential risk is that a person may not want to participate in the study and may feel coerced to do so. Therefore, to minimize this type of risk, all informed consent contact with potential participants will come through the study staff only, and all NH staff participation discussions and decisions will be kept confidential.

8b. Data Safety Monitoring

Is there a Data Monitoring Committee (DMC) or Board (DSMB)?

If yes, describe its role, if it is independent of the sponsor or research team, the make-up of the Board and their qualifications, and how often the Board will meet.

1 Frequency of Data and Safety Monitoring

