FOR RESIDENTS WITH LIKELY MILD ADRD (BIMS SCORE ABOVE 10) BUT NO LAR, THE NURSING HOME LEADERSHIP TEAM AND STUDY STAFF WILL GO DIRECTLY TO THE RESIDENT TO INVITE THEIR PARTICIPATION AND SCREEN THEIR CAPACITY TO CONSENT USING THE SAME PROCESS DESCRIBED ABOVE.

All above procedures apply to securing consent for the study team to have access to NH resident personally identifiable data. We note that because the LOCK sleep program does not include any activities that are outside of standard NH practice, NH staff will be free to enroll any NH residents that they believe will benefit into the LOCK sleep program regardless of resident consent status; but the NH leadership team will only share with researchers data from residents who are consented for the study.

NH Staff Consent

The NH leadership team or their designees will provide to all NH staff an IRB-approved study introduction letter (including option to opt out within two weeks if they do not wish to be contacted by study staff). Contact information of those NH staff not opting out will be shared with UA study staff. We will request of the IRB a waiver of consent for screening purposes regarding the sharing of these contact information.

UA Study staff will contact NH staff (via email and/or phone, see next paragraph) to invite them to participate in mid-implementation phone interviews. Study staff will also contact NH staff to invite them to participate in post-implementation interviews (phone). The list of NH staff who agree and decline interview participation will remain confidential to protect NH staff from any possible coercion to participate (see 1.3.b. Protection Against Risks).

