NH leadership team training: The NH leadership team will complete NIH-required computer-based trainings (on the protection of human research participants, HIPAA, and Good Clinical Principles). Study staff will also provide a 2-hour training on procedures to protect vulnerable subjects, as follows: proper procedure for, and importance of only using IRB-approved procedures and letters when sending study opt-out letters to LARs; proper procedures for maintaining security and privacy of data packages mailed to the University of Alabama project office; proper procedures for avoiding coercion or appearance of coercion of research participation when working with NH staff (e.g., not asking staff about research interview participation); proper procedures for assisting in telephone appointment arrangements and providing logistical support when study team members conduct telephone-based NH resident consenting and capacity to consent assessment; importance of only study team members conducting actual consent procedures of anyone (LARs, NH residents, NH staff);

importance of only properly trained NH leadership team members participating in study procedures. [name] (via zoom teleconference) will work together to provide training on the appropriate application of actigraphs and Fitbits to promote comfort and prevent adverse experiences, as well as appropriate assessment equipment maintenance and data mailing.

NH staff training: As part of the intervention training, NH staff will be trained by their NH leadership teams or their trained designees on proper use and placement of actigraphs and Fitbits, verbal and behavioral signs of distress that might indicate actigraph/Fitbit-related discomfort/distress, and appropriate modification techniques to try to relieve such distress. NH staff will be informed that the devices should be removed in the unlikely event that distress behaviors are not relieved by modification techniques. NH staff will be trained on importance of NH resident autonomy, and will be engaged in a discussion of how to assess for and honor NH resident assent or lack thereof with regard to the devices.

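### For residents with no LAR, the plan has the home's leadership team join study staff in the invitation and capacity screen, contrary to its own rule that consent contact is for study staff only

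*Combined protocol and SAP*

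**What the plan says.** **The rule.** Section 3(b), in the list of what leadership teams may and may not do, says that "NH leadership teams will not engage in research study tasks which will be completed exclusively by research study team members". The first task on that reserved list is "Conducting informed consent with staff, LARs, and residents". The permitted role in resident consent is "Assisting in telephone appointment arrangements and logistical support so that study team members can conduct telephone-based informed consent". Leadership training, in Section 3(b) and again in 1.3.b of the Data and Safety Monitoring Plan (DSMP), teaches that only study team members carry out consent with LARs, residents or staff.

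**The safeguard.** Section 8, item 8a, says of both residents and staff that "a potential risk is that a person may not want to participate in the study and may feel coerced to do so". Its answer is that "all informed consent contact with potential participants will come through the study staff only". DSMP 1.1 repeats this.

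**The no-LAR route.** For residents with likely mild dementia (BIMS above 10) and no LAR, Section 7(n), Section 2, item 2, says that "the nursing home leadership team and study staff will go directly to the resident to invite their participation and screen their capacity". The same sentence closes the resident consent steps in Section 12, item 1. It stands in capitals in DSMP 1.3.a: "THE NURSING HOME LEADERSHIP TEAM AND STUDY STAFF WILL GO DIRECTLY TO THE RESIDENT TO INVITE THEIR PARTICIPATION AND SCREEN THEIR CAPACITY". All three versions end by referring back to the procedure already set out for residents who have a LAR.

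**Who is on the team.** Section 3(b) defines the leadership team as including at least the Director of Nursing, the administrator, the staff educator and the QI designee.

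**The concern.** The plan names coercion of residents as a study risk and offers one main protection: the people who run the home do not take part in consent contact. The no-LAR sentence makes those people joint actors in two steps, the invitation and the capacity screen.

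The group matters because of what it lacks. Section 7(n) presents LAR oversight as the protection for residents who may not have capacity. With a LAR, an introduction letter, an opt-out period and the LAR's own consent come before anyone approaches the resident. None of these steps is described for a resident without a LAR, so the joint invitation is the first study contact that the plan describes. The study-staff-only rule does more of the protective work here than in the LAR route.

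**Working it through.** No arithmetic applies. The question is who performs each step, so the passages are set side by side.

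| Step | General rule and LAR route | No-LAR sentence |
|---|---|---|
| Invite the resident | Study staff; Section 8 item 8a and DSMP 1.1 route all consent contact through them | Leadership team and study staff |
| Screen capacity | Study staff member, by telephone (Section 7(n) Step 2, DSMP 1.3.a, Section 12) | Leadership team and study staff |
| Go through the consent form | Study staff member | By reference to the LAR route: study staff |
| Arrange the call, quiet setting, printed form, copying and mailing | Leadership team | By reference: leadership team |

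1. **Invitation.** Inviting a resident to take part is consent contact on any ordinary reading. The rule that all such contact comes through study staff only, and a sentence in which leadership also invites, cannot both be followed. This is the clearest conflict.

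2. **Capacity screen.** In the procedure that the sentence refers to, the study staff member gives the information, asks the orientation and understanding questions, and takes the resident through the form. Leadership has no part in the questions or in judging the answers. The no-LAR sentence therefore assigns leadership a task that its own reference does not.

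3. **Setting.** Section 3(b) says research staff will not enter the homes because of infection control. If leadership and study staff are to go directly to the resident, only leadership can be there in person. A literal reading puts a manager in the room as co-inviter, with study staff on the telephone.

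4. **A linked gap.** Section 7(n) says in three places that LARs are always contacted before the resident: Section 1, Category 1; Section 2, item 3(c); and Section 2, item 7. None makes an exception for a resident who has no LAR. The no-LAR route cannot satisfy these statements as written.

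5. **Likely origin.** A note in Section 1 says capitals mark amendment changes, and the DSMP version is in capitals. This suggests that the sentence was added later and the older rules were not revised to match. That is an inference, and the conflict does not depend on it.

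**The case against.** The best reply is that this is loose drafting with a harmless meaning. Each of the three sections opens by saying that all consents are conducted by a trained, IRB-approved study staff member, and the no-LAR sentence falls under that statement. Its closing reference points to a procedure in which study staff screen and leadership supports. Because research staff cannot enter the homes, someone from leadership must be on site for the call to happen. On this reading the sentence means only that the LAR step is skipped and the usual division of labour applies. The plan also accepts some outreach by leadership elsewhere, since leadership mails the introduction letter to LARs.

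Much of this stands. It is a reasonable guess at what was meant, and it is why the point concerns wording and not a faulty consent design. It does not remove the conflict. The sentence gives leadership two verbs, invite and screen, that the referenced procedure withholds from it, and a home could follow either text in good faith. The mailed letter differs because it is an approved document, sent to the LAR and carrying an opt-out.

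A reader might infer more: that managers obtain these residents' consent, or that their presence raises acceptance or the share judged capable and so distorts Aim 2's test of consent methods. The documents support neither. No passage has leadership obtaining consent or judging capacity answers. The analysis plan in Section 3(d) names no acceptance or capacity rate that could be distorted. Nor does the text show that these are the least protected residents. The route is limited to BIMS above 10, and the resident must answer every capacity question appropriately before signing.

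**Conclusion.** The conflict is real and stands in the current text in three places. The no-LAR sentence contradicts the reservation of consent to study team members (Section 3(b), DSMP 1.3.b) and the coercion safeguard (Section 8 item 8a, DSMP 1.1), and it departs from the procedure it cites. Loose drafting is a likely explanation. Even so, a home that acted on the words as written would breach the plan's stated protection for residents who have no LAR to oversee entry.

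The size cannot be calculated. The plan expects to consent 70 residents and to have 57 complete, but gives no number or share without a LAR, and any count would be a guess. The conclusion does not need one. It rests on reading an invitation to take part as consent contact. Sample size, outcomes and planned analyses are unaffected, so the correction is worth making for participant protection and consistent conduct across the three homes.

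**What to change.** - In Section 7(n), Section 2, item 2, in DSMP 1.3.a and in Section 12, item 1, reword the no-LAR sentence to say that study staff alone invite the resident and screen capacity by telephone. Limit the leadership team to arranging the call, providing the quiet setting and handling the printed form, as in the LAR route, with no part in the invitation, the answers or the decision.
- In Section 7(n), add the no-LAR exception to the three statements that LARs are always contacted first (Section 1, Category 1; Section 2, items 3(c) and 7).

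The cost is a wording change in six places within one amendment. Study staff already conduct these calls for residents with a LAR, so the change needs no new staff, training or data collection. Recording and reporting results by consent route would be optional; the conflict does not require it.

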NH Resident Data will be collected for consented NH residents from Brief interview of family/friends (see attachment), NH staff interview of the resident (see attachment), NH staff ratings (clinical global assessments of change in overall sleep quality and sleep-related conditions - see Appendix; NH staff sleep reports - see attachment); through primary data collection (actigraph/Fitbit measurements; these are wristwatch-sized devices worn on the wrist); through medical records (age, diagnoses, medical history, and medications); and through NH secondary data from the Minimum Data Set (MDS; all Medicare-reimbursed NHs are required to collect MDS assessments on all residents; the MDS contains information on resident medical conditions, functioning, cognition, psychotropic and pain/analgesic medication use, activities of daily living decline, and sleep-, mood-, and activity-related items). Table 1 summarizes the primary and secondary outcomes and data sources.

NH Staff Data: staff interview data will be collected via audiorecorded qualitative interview (see Appendix).

Data Collection Procedures:

NH Resident Primary Research Data Collection: will consist only of actigraph/fitbit data.

We will measure total sleep time (TST) with data from Micro-Mini Motionlogger Actigraphs (Ambulatory Monitoring Inc., Ardsley, NY).[87] We will define nighttime as 10pm to 6am and will compute TST as the total number of minutes asleep during a nighttime period. We will measure sleep for 7 days at each measurement period (see Figure 2) to obtain reliable measurements and will use the average TST across this period. We will also examine the following: wake after sleep onset (total number of minutes awake during nighttime), how often the resident awoke during the nighttime, sleep efficiency (the ratio of

minutes asleep to minutes awake over the period), and sleep fragmentation (an index of restlessness computed as the percentage of one-minute epochs scored as awake). Sensitivity of actigraph measurement for sleep is very good (actigraphy = sleep when polysomnography = sleep was 0.97). [88]

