Study staff will provide a 2-hour virtual training on procedures to protect vulnerable subjects, as follows: proper procedure for, and importance of only using IRB-approved procedures and letters when sending study opt-out letters to LARs; proper procedures for maintaining security and privacy of data packages mailed to the University of Alabama project office; proper procedures for avoiding coercion or appearance of coercion of research participation when working with NH staff (e.g., not asking staff about research interview participation); proper procedures for assisting in telephone appointment arrangements and providing logistical support when study team members conduct telephone-based NH resident consenting and capacity to consent assessment; importance of only study team members conducting actual consent procedures of anyone (LARs, NH residents, NH staff); importance of only properly trained NH leadership team members participating in study procedures.

[name] will work together to provide virtual training on the appropriate application of actigraphs and Fitbits to promote comfort and prevent adverse experiences, as well as appropriate assessment equipment maintenance and data mailing. For example, the NH leadership team will be trained on the appropriate actigraph/fitbit cleaning as described in the previous subsection (Staff Training). They will also be taught that actigraphs/fitbits should only be applied to dry, clean skin. The skin should be gently washed with the skin cleanser approved for facility use for the nursing home resident (typically a non-soap cleanser such as cetaphil, but this may differ depending upon the specific resident), gently rinsed with a clean damp washcloth, and then carefully dried to avoid trapping moisture between the actigraph/fitbit and skin. Similarly, when the actigraph/fitbit is removed in the morning, the skin should be again cleansed and dried.

NH Staff Intervention Training and Intervention Implementation:

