d) Describe how data analysis will be performed (statistical tests, methods of evaluating data) and indicate the smallest group/unit for which separate reporting will occur. For studies involving a questionnaire, if data and reliability information are available, please describe or provide references. (Page numbers from a sponsor's protocol/grant may be referenced in this section).

Data analysis for this pilot study (R61 phase) will inform revisions to our upcoming randomized controlled trial (R33 phase). We will conduct a preliminary assessment of our outcome measures, particularly our primary outcomes from the actigraphy TST measurements and fitbit sleep time measurements, and secondary outcomes from the MDS and our supplementary sleep data (see Table 1). We will examine ranges, indicators of variability (change over time), and rates of missing data. We will also examine indicators by demographic characteristics (e.g., age, gender) and level of dementia severity (mild, moderate, severe). To test the sensitivity of our secondary outcomes and supplementary sleep data to individual differences in TST and change in TST, we will preliminarily examine the relationships of these with average TST and variability in TST.

For the qualitative interviews, all interviews will be audio recorded and transcribed and [name] will guide the experienced qualitative team in using a rapid appraisal template analysis,[112,113] a rigorous technique for thematically organizing and analyzing data. The analysis will identify, in particular, areas for modifications to the LOCK sleep program training. Interviews will also inform our decision of whether or not to include Fitbits as part of the subsequent randomized controlled trial (R33 phase), based on staff members' impressions of the value of Fitbits and their impressions of the feasibility of using both devices. We will also modify interview guides (see Appendix) for the next phase, as necessary.

[Selected References]

112.King N. Using templates in the thematic analysis of text. In: Essential Guide to Qualitative Methods in Organizational Research. London: SAGE Publications Ltd; 2004.

113.Beebe J. Basic Concepts and Techniques of Rapid Appraisal. Human Organization. 1995;54(1):42-51.

* * * Radioisotopes or Radiation Machines * * *

4) Radioisotopes or Radiation Machines

Please note: For projects requiring radiation procedures, please contact the UA Environmental Health and Safety Office at [name]

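### Sleep efficiency is defined as an odds (asleep to awake), and the measure labelled wake after sleep onset counts all wake from 10pm to 6am with no onset rule

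*Combined protocol and SAP*

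**What the plan says.** All the definitions stand in one paragraph of the Combined protocol and SAP, Section 3(b) Study Procedures, under Data Collection Procedures.

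- Window and primary measure: "We will define nighttime as 10pm to 6am and will compute TST as the total number of minutes asleep during a nighttime period". For each 7-day measurement period the plan "will use the average TST across this period".
- Wake measure, listed among those also to be examined: "wake after sleep onset (total number of minutes awake during nighttime", where the bracket is the definition.
- Sleep efficiency: the ratio of "minutes asleep to minutes awake over the period".

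The averaging rule is stated for TST only. No bedtime, sleep-onset rule or other denominator for efficiency appears anywhere in the supplied text. Section 3(d) describes the analysis: "We will examine ranges, indicators of variability (change over time), and rates of missing data". It says that the pilot results will inform revisions to the later randomised trial (the R33 phase), and it does not redefine these measures.

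**The concern.** Each measure carries a label that its stated computation does not match. A reader takes sleep efficiency to be a share of the night spent asleep; the written formula divides by wake instead. A reader takes wake after sleep onset to begin at onset; the written formula begins at 10pm.

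This matters because testing and refining the research methods is one of the pilot's two specific aims (Section 2(b)). If ranges and changes over time are tabulated as defined, the efficiency figures will be dominated by residents who already sleep well, and their average can disagree in direction with average TST. The wake figures cannot separate a late first sleep from waking during the night. Uncorrected, both definitions could pass into the R33 trial.

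**Working it through.** The plan states no figure for these measures, so there is none to reproduce. The check is arithmetic on its definitions.

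**Inputs.** From the protocol: window 10pm to 6am = 8 x 60 = 480 minutes; S = minutes asleep in the window (TST); A = minutes awake. With every minute scored, A = 480 - S. The documents give no mean or SD for TST, so the values of S below are illustrative.

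**Step 1: scale of efficiency as written.** Ratio = S / (480 - S); share asleep = S / 480.

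| S (min) | Ratio as written | Share asleep | Ratio gain from +30 min | Share gain from +30 min |
|---|---|---|---|---|
| 240 | 240/240 = 1.00 | 50.0% | 0.29 | 6.25 points |
| 300 | 300/180 = 1.67 | 62.5% | 0.53 | 6.25 points |
| 360 | 360/120 = 3.00 | 75.0% | 1.33 | 6.25 points |
| 420 | 420/60 = 7.00 | 87.5% | 8.00 | 6.25 points |
| 480 | 480/0, undefined | 100% | - | - |

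The same half hour of extra sleep counts 1.333 / 0.286 = 4.7 times as much from 360 minutes as from 240.

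**Step 2: meaning of the period.** Take seven nights of 240, 270, 300, 300, 330, 360 and 390 minutes asleep.

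- Nightly ratios: 1.000, 1.286, 1.667, 1.667, 2.200, 3.000, 4.333; their mean is 15.152 / 7 = 2.16.
- Ratio of 7-day totals: 2190 / (3360 - 2190) = 2190 / 1170 = 1.87.
- Share asleep: 2190 / 3360 = 65.2%, whether averaged nightly or pooled.

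**Step 3: direction when averaged across residents.** Resident A goes from 240 to 300 minutes, resident B from 390 to 360.

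- Mean TST: (240 + 390)/2 = 315, then (300 + 360)/2 = 330, a rise of 15 minutes. As a share, 15/480 = +3.1 points.
- Mean ratio: (1.000 + 4.333)/2 = 2.67, then (1.667 + 3.000)/2 = 2.33, a fall of 0.33.

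Treating each S as a 7-day mean from fully scored nights gives the same numbers, so pooling over the week does not remove the reversal.

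**Step 4: the wake measure.** As written it is A, which equals 480 - S when scoring is complete. Suppose two residents each sleep 360 minutes. One has not slept before 10pm, first sleeps at 11:30pm and is later awake 30 minutes: 90 + 30 = 120. The other is asleep at 10pm and later awake 120 minutes. Both score 120 as written; by the label they have 30 and 120. For a resident who already slept before 10pm, by contrast, wake inside the window is wake after onset and is rightly counted. The measure therefore can include wake before onset, but need not.

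**The case against.** The strongest reply is that an odds is a legitimate, computable quantity. That efficiency is usually a proportion is general measurement knowledge and is not stated in the documents. If the ratio is taken over seven days, a single resident's value o converts back to a share as o/(1+o). This stands for one resident. It does not help once values or changes are averaged across residents, and it does not settle which period is meant.

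A second reply is that Section 3(d) announces no contrast of mean efficiency and does not name either measure. That is correct: the harm follows only if the measures are summarised as defined. The reversal uses two chosen residents moving in opposite directions, and nothing in the documents allows its frequency to be estimated.

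Three stronger readings are tempting, and the documents do not support them.

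- A reader might infer that the wake measure always contains wake before onset. The protocol fixes a clock window and gives no bedtime. A resident who slept at 9pm, woke at 9:50pm and slept again at 10:40pm contributes 40 minutes of true wake after onset. For the same reason, starting the count at the first scored sleep after 10pm would not be a safe repair, because it would drop those 40 minutes.
- A reader might infer that the planned correlations are partly circular, since the plan says "we will preliminarily examine the relationships of these with average TST and variability in TST". That sentence concerns secondary outcomes and supplementary sleep data. Whether the latter includes these actigraphy measures depends on Table 1, which was not supplied; staff and family reports are at least as natural a reading.
- A reader might extend the complaint to "sleep fragmentation (an index of restlessness computed as the percentage of one-minute epochs scored as awake". That index is openly defined by its computation, so a different name would be a matter of preference.

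Finally, operational definitions may sit in Table 1 or the appendix measures, which are listed as attachments. That possibility remains open.

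**Conclusion.** Minor, but wrong as written: two stated rules yield values that do not match their labels, and no supplied text corrects either. The conclusion about efficiency follows from the formula alone. The sizes in the illustrations rest on chosen sleep times and complete scoring; they show what can happen, not how often. The conclusion about wake rests on the absence of an onset rule.

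A reader might go further and infer that the pilot's main sleep result is compromised. It is not. TST is defined separately and consistently, the number of awakenings and the rates of missing data are untouched, and no sample size or error rate depends on these measures.

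**What to change.** Amend the actigraphy paragraph in Section 3(b).

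1. Define sleep efficiency as 100 x minutes asleep / scored minutes in the 10pm-6am window, averaged over nights as for TST. Scored minutes are the safer denominator: Section 3(b), NH Leadership Team Training, describes skin care "when the actigraph/fitbit is removed in the morning" and gives no application time, so a window may not be fully scored. Add that with complete scoring this is a rescaling of TST and not separate evidence.
2. Relabel the wake measure as total nighttime wake (10pm-6am). Keep the term wake after sleep onset only if an onset rule that allows for sleep before 10pm is specified.
3. Check that Table 1 and the appendix measures agree with the revised wording.

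The cost is a few sentences and a recomputation from epochs already collected. No new data are needed.
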